4.6.3 Deaths, Other Serious Adverse Events, and Other Significant Adverse Events

All deaths during the study, including the post treatment follow-up period, will be listed by patient, to include the primary cause of death. Serious TEAEs and other significant AEs, including those that led to withdrawal, interruption, or dose reduction of each

study drug and those classified as CTCAE Grade 3 or higher will be provided in separate patient data listings.

4.6.4 Clinical Laboratory Evaluation

All descriptive summaries of laboratory results will be based on data analyzed by the central or local laboratory and presented in Système International (SI) units, as suggested by the Center for Biologics Evaluation and Research and the Center for Drug Evaluation and Research *Position on Use of SI Units for Lab Tests* (Oct 2013). All data will be included in by-patient data listings. Laboratory measurements identified as abnormal (i.e., outside the normal range) will also be listed separately by patient, laboratory test, and unit. In addition, normal ranges provided by the central laboratory will be presented in a separate listing.

Clinical laboratory measurements, including serum chemistry, hematology, and coagulation will be summarized by dosing regimen. Descriptive statistics will be presented for observed values and changes from baseline at each visit where parameters were scheduled to be collected per the clinical study protocol.

Where applicable, laboratory results will be classified as “low,” “normal,” or “high” with respect to the parameter-specific reference ranges (i.e., below the lower limit of the normal range, within the normal range, or above the upper limit of the normal range). Three-by-three contingency tables will be presented for each laboratory parameter to summarize the shift from the baseline category to the worst post-baseline measurement, defined as the value numerically farthest outside of the normal range across all post-baseline visits through the end of the study.

Summary results will include the count and percentage of patients within each shift category and treatment group.

The cumulative number and percentage of patients with liver function test abnormalities meeting drug-induced liver injury (DILI) criteria will be summarized by dosing regimen. Patients meeting DILI criteria will also be presented in a patient data listing.

In addition, creatinine clearance will be calculated by the Cockcroft-Gault formula. For males, the creatinine clearance in mL/min is calculated as $[(140 - \text{age}) \times \text{weight (kg)}] / [72 \times \text{serum creatinine (mg/dL)}]$. For females, the creatinine clearance in mL/min is calculated as $0.85 \times$ the male value. The mean change from baseline over time for creatinine and creatinine clearance will be presented graphically over time by dosing regimen and over all patients combined.

Where applicable, hematology, chemistry, and coagulation results for select parameters will be assigned a toxicity grade based on the U.S. Department of Health and Human Services *Common Terminology Criteria for Adverse Events (CTCAE)*, version 5.0 (27 Nov 2017). If the quantitative criteria for grading are equivalent for two grades and the differentiation is described by clinical interventions, the clinical intervention component will not be considered and the highest CTCAE grade will be assigned. Similarly, death related to AE (i.e., Grade 5) cannot be determined with available laboratory-based data collection and, thus, will not be summarized as a category. Laboratory parameters that include multiple sets of criteria for each direction (e.g.,

separate criteria for potassium measures to assess hyperkalemia and hypokalemia) will be summarized separately to reflect each set of criteria.

Five-by-five contingency tables will be presented for laboratory tests where toxicity grading can be applied, to summarize the shift from the baseline grade to the worst post-baseline grade. Grades will be presented as none (Grade 0; i.e., measurements did not meet any CTCAE criteria for Grades 1 through 4), mild (Grade 1), moderate (Grade 2), severe (Grade 3), or life-threatening (Grade 4). Summary results will include the count and percentage of patients within each shift category.

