5.7.1.2. Hematopoietic Growth Factors

The prophylactic use of hematopoietic growth factors is prohibited unless the patient experiences an AE. Granulocyte colony-stimulating factor (G-CSF) agents may be administered in response to Grade ≥3 neutropenia (Table 7). The American Society of Clinical Oncology (ASCO) clinical practice guidelines should be followed (Smith 2015). Hematopoietic growth factors may not be used within 21 days of screening.

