4.1.2 Summarization by Visit

Data summarized by study visit will be based on the nominal, scheduled visit label as reported on the eCRF. Data collected for the last patient visit completed will be summarized separately, and this summary will be labeled as “End of Treatment.”

Data collected at unscheduled visits will not be included in by-visit summaries but will be considered when endpoint derivations potentially include multiple visits (e.g., determination of baseline value, determination of worst post-baseline value, etc.). All data will be included in patient listings.

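### The low/normal/high laboratory shift tables place a patient who has both low and high values in one category only, and for neutrophils the rule favours high

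*SAP*

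**What the plan says.** SAP 4.6.4 classifies each result as low, normal or high against its reference range and then states: "Three-by-three contingency tables will be presented for each laboratory parameter to summarize the shift from the baseline category to the worst post-baseline measurement". That worst measurement is "defined as the value numerically farthest outside of the normal range across all post-baseline visits through the end of the study". Nothing in the rule separates the two directions. SAP 4.1.2 leaves unscheduled visits out of by-visit summaries but uses them for derivations that span visits, including "determination of worst post-baseline value, etc". A single unscheduled reading can therefore decide the category.

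The same section plans a second set of tables: "hematology, chemistry, and coagulation results for select parameters will be assigned a toxicity grade" under CTCAE version 5.0, and "Five-by-five contingency tables will be presented for laboratory tests where toxicity grading can be applied". Parameters with criteria in both directions "will be summarized separately to reflect each set of criteria". The graded tables thus respect direction; the low/normal/high tables do not. The parameters to be graded are not named.

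Protocol 5.7.1.2 allows growth factor on study: G-CSF "agents may be administered in response to Grade ≥3 neutropenia".

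**The concern.** Cytopenia is the severe toxicity to watch with this regimen. Protocol Table 1 (the earlier lymphoma study) gives Grade 3/4 thrombocytopenia in 13 of 25 and 7 of 30 patients, and neutropenia in 10 of 25 and 9 of 30. A reader of a shift table expects the low column to count everyone who went low. Under this rule, a patient who drops below range and later rises far enough above it leaves the low column. For neutrophils, the patients most exposed to this are those whose low count led to growth factor.

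SAP 4.8 says the study stopped after Phase 1b, so the tables describe dose cohorts planned at 3 to 6 patients. Moving one patient between cells then shifts a percentage by 1/6 = 17 to 1/3 = 33 points. For any parameter outside the graded set, the three-by-three table is the only shift summary.

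**Working it through.** The plan gives no figure to reproduce here; the check applies its rule directly.

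**Inputs.** The rule is from SAP 4.6.4. Protocol Table 7 puts Grade 4 neutropenia below 0.5 x10^9/L and Grade 4 thrombocytopenia below 25 x10^9/L, so nadirs of 0.49 and 24 are just inside Grade 4. Reference ranges are not in the documents; those below are assumptions, varied to show the effect.

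**Formula.** With lower limit L and upper limit U, a nadir lies L − nadir below the range and a peak lies peak − U above it. The patient is tabulated as high when peak − U > L − nadir, that is, when peak > U + (L − nadir). Since the nadir cannot be below zero, the low-side distance never exceeds L. The high-side distance has no bound.

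**Thresholds (x10^9/L).**

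| Parameter | Assumed range | Nadir | Peak must exceed | Multiple of U |
|---|---|---|---|---|
| Neutrophils | 1.5–8.0 | 0.49 | 8.0 + 1.01 = 9.01 | 1.126 |
| Neutrophils | 1.8–7.5 | 0.49 | 7.5 + 1.31 = 8.81 | 1.175 |
| Neutrophils | 2.0–7.0 | 0.49 | 7.0 + 1.51 = 8.51 | 1.216 |
| Platelets | 130–400 | 24 | 400 + 106 = 506 | 1.265 |
| Platelets | 150–400 | 24 | 400 + 126 = 526 | 1.315 |
| Platelets | 150–450 | 24 | 450 + 126 = 576 | 1.280 |

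Pairing the neutrophil limits differently widens the threshold to between 7.0 + (1.5 − 0.49) = 8.01 and 8.0 + (2.0 − 0.49) = 9.51. The multiples of U (1.144 and 1.189) stay inside the span shown. Even a neutrophil nadir of zero is displaced above 9.5, 9.3 or 9.0 on the three ranges (1.19, 1.24 and 1.29 times U).

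**Worked patients.**

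- Neutrophils 4.0 at baseline, then 0.3, then 12.0, range 1.8–7.5. The distances are 1.8 − 0.3 = 1.5 low and 12.0 − 7.5 = 4.5 high. The patient is shown as normal to high; the low value does not appear in the table.
- Platelets 220, 20, 560, range 150–400. The distances are 130 low and 160 high, so the patient is shown as high.
- Platelets 220, 20, 500, same range. The distances are 130 low and 100 high, so the patient stays low, and here it is the high value that goes uncounted.

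**With the directions separated.** The first patient is low in the table of lowest values and high in the table of highest values. The five-by-five grade table shows Grade 4 for that patient under either rule, provided neutrophils are among the graded parameters.

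**The case against.** A reader might infer that severe neutropenia or thrombocytopenia could disappear from the report. The documents do not support that. The three-by-three table carries no severity: a value just under the lower limit and a Grade 4 value are both low. Severity is reported elsewhere:

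- the five-by-five tables run to the worst post-baseline grade, which a later high count cannot erase;
- SAP 4.6.4 lists every out-of-range value by patient;
- Protocol 9.7 has clinically significant Grade 3 and 4 laboratory abnormalities listed and summarized;
- SAP 4.6.2 and 4.6.3 give adverse events by grade, DLT incidence and listings of Grade 3 or higher events.

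The unnamed list of graded parameters weakens this only slightly. The SAP ties the five-by-five tables to tests that can be graded, Protocol Table 7 itself gives count thresholds for these cytopenias, and nothing suggests neutrophils or platelets would be left out.

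Three further points stand. A trivial rise is not enough: the neutrophil peak must pass the upper limit by about 13% to 22% in the cases above. For platelets the rebound must be larger still, and the growth factors the protocol permits (G-CSF and GM-CSF) are directed at neutropenia, so no specific cause of such a rebound is documented. And a table that follows its stated definition is not erroneous; a reference-range category and a CTCAE grade are different measures and need not agree.

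It is also fair to say that no endpoint or dose decision uses these tables. DLTs rest on the criteria in Protocol 5.5.3.1, the analysis is descriptive, and in cohorts this small the listings show each patient.

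None of this changes what the rule does inside its own table. It still drops one of two real excursions, and for a count with a floor at zero it tends to drop the low one.

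**Conclusion.** The point holds as a minor defect in one set of safety tables. The three-by-three tables can under-count patients with a low value, most readily for neutrophils, where a later value of roughly 1.1–1.2 times the upper limit displaces a nadir of 0.49. For platelets the same arithmetic applies at about 1.3 times the upper limit, but as a possibility without a documented mechanism.

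The thresholds rest on assumed reference ranges. The number of patients affected cannot be derived: growth factor is permitted, not required, and the documents give no expected rate of use or of rebound. The conclusion concerns the low/normal/high classification only; it is not a loss of the severe-cytopenia signal.

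**What to change.** In SAP 4.6.4, for each parameter with both a lower and an upper reference limit, replace the single shift table with two: baseline category to the category of the lowest post-baseline value, and baseline category to the category of the highest. Keep unscheduled values in both derivations, as SAP 4.1.2 already provides. A patient with both excursions is then counted in both tables, and a footnote should say so. Parameters with only one limit keep a single table.

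The cost is a small programming change and a longer table; no new data are needed. While the section is open, naming neutrophils and platelets among the graded parameters would remove the remaining doubt about the five-by-five tables, but the fix does not depend on it.

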4.6.5 Vital Signs, Physical Findings, and Other Observations Related to Safety

4.6.5.1 Vital Signs

Descriptive statistics for vital sign parameter measurements will be presented for results and change from baseline at each visit where parameters were scheduled to be collected.

4.6.5.2 12-Lead Electrocardiogram

Descriptive statistics will be presented for observed values and changes from baseline at each visit where parameters were scheduled to be collected. All 12-lead ECGs will be conducted in triplicate. The average of the triplicate ECG interval parameters will be summarized by treatment regimen.

Twelve-lead ECGs will be classified by the investigator as “normal,” “abnormal, not clinically significant,” or “abnormal, clinically significant.” The worst classification for each set of triplicate 12-lead ECGs will be used for analysis. Three-by-three contingency tables will be presented to summarize the shift from the baseline category to the worst post-baseline value. Summary results will include the count and percentage of patients within each shift category and treatment group.

Prolonged QTc intervals will be summarized as QTc measurements (msec) that are >450, >480, and >500 msec averaged over each set of triplicate 12-lead ECGs at each visit where ECG is routinely collected per the clinical study protocol. Change from baseline categories will also be summarized for measurements that represent a change >30 or >60 msec relative to the baseline value. Summary results will include the percentage of patients within each category and treatment group.

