1.6.2. Potential Risks

HDAC inhibitors are potent inducers of the EBV lytic cycle; the production of infectious virus by virtue of HDAC inhibitor-mediated induction of the tumor lytic cycle is a clinically documented AE described in a monotherapy clinical trial with the HDAC inhibitor romidepsin (ISTODAX® [romidepsin] Prescribing Information 2021). However, this potential safety issue can be abrogated by the coadministration of ganciclovir. In the Phase 1b/2 VT3996-201 study, patients' EBV genome levels are monitored in a serial fashion. No cases of EBV reactivation have been reported to date, indicating that this combination is preventing EBV viremia.

Pertaining to the coadministration of nanatinostat and valganciclovir, both drugs exhibit overlapping toxicities (ie, thrombocytopenia and renal dysfunction) that may be increased in frequency or severity in combination. In addition, other toxicities were reported in prior clinical studies for one or both agents including fatigue, atrial fibrillation, nausea/vomiting, anemia, leukopenia, and neutropenia.

Toxicities reported for other HDAC inhibitors include thrombocytopenia, QTc prolongation, neutropenia, anemia, fatigue, and diarrhea (Gryder 2012). Medications with a known risk of prolonging the QT interval should be avoided (Section 5.7.4).

Toxicities reported for pembrolizumab include immune-mediated adverse reactions (irAEs) such as pneumonitis, colitis, hepatitis, endocrinopathies, nephritis with renal dysfunction, and dermatologic adverse reactions, as well as gastrointestinal events (nausea, decreased appetite, constipation, and abdominal pain). Patients receiving nanatinostat and valganciclovir in combination with pembrolizumab will be closely monitored for any evidence of irAEs as well as renal dysfunction and enhanced gastrointestinal toxicity.

Further information about the safety profile of nanatinostat as a single agent and in combination with valganciclovir can be found in the current IB. For pembrolizumab, please consult the prescribing information (Keytruda [pembrolizumab] Prescribing Information 2023).

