Grade 4 anemia	 Hold both study drugs. Transfuse. Once anemia resolves to ≤Grade 2 (≥8.0 g/dL), resume nanatinostat at the planned dose and valganciclovir at a lower dose as follows: Decrease 900 mg twice daily to 900 mg daily; decrease 900 mg daily to 450 mg daily; decrease 450 mg daily to 450 mg every 2 days; decrease 450 mg every 2 days to 450 mg twice weekly) If anemia persists, then decrease nanatinostat daily dose to the next lowest nanatinostat dose level. If recurs, interrupt both drugs and discuss with the study's Medical Monitor. 	Maintain dose and schedule.
Febrile neutropenia (ANC <1.0 × 10 ⁹ /L, with a single temperature of ≥38.3°C or a sustained temperature of ≥38°C for more than 1 hour)	 Interrupt nanatinostat/valganciclovir dosing. Resume nanatinostat/valganciclovir at the same doses when ANC ≥1.0 × 10⁹/L. Use of growth factors (G-CSF, GM-CSF) are permitted per the ASCO 2015 clinical practice guidelines (Smith 2015). 	Withhold until resolution to Grade 0 or 1.
QTc prolongation	 For QTc interval >480 msec and <500 msec: Check magnesium and potassium levels and correct any abnormalities. If possible, stop any medications that may prolong the QTc interval. Decrease nanatinostat to the next lowest nanatinostat dose level. Resume nanatinostat/valganciclovir at the initial dose in the next cycle provided that the QTc interval improves to ≤470 msec at the start of that cycle. Otherwise continue nanatinostat at the next lowest nanatinostat dose level. 	Maintain dose and schedule.

NCI CTCAE v5.0	Recommended Dose Modifications for Nanatinostat and	Recommended Dose Modifications
Toxicity Grade	Valganciclovir	for Pembrolizumab
	 For QTc interval >500 msec: Check magnesium and potassium levels and correct any abnormalities. Interrupt nanatinostat/valganciclovir dosing and stop any medications that may prolong the QTc interval. If the QTc interval improves to ≤470 msec just prior to the start of the next cycle, resume nanatinostat/valganciclovir at the initial dose. If no other cause of QTc prolongation is identified, decrease dose of nanatinostat to the next lowest nanatinostat dose level. Otherwise continue to hold nanatinostat/valganciclovir for as long as necessary. 	

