7.3.4. End of Treatment

At the time patients discontinue study treatment, a visit should be scheduled as soon as possible and within 14 days after the last dose of study drug, at which time all assessments listed for the End of Treatment (EOT) visit will be performed. The EOT visit will be recorded in the eCRF with the date and reason for stopping the study treatment. At a minimum, all patients who discontinue study treatment, including those who refuse to return for a final visit, will be contacted for follow-up safety evaluations 30 and 90 days following the last dose of study drug(s).

The assessments to be performed at EOT are listed in the Schedule of Events provided in Table 11.

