7.4.2.5. Cardiac Assessments: Electrocardiograms (ECGs)

All 12-lead ECGs will be conducted in triplicate. Average QTcF will be calculated to confirm eligibility. ECG tracings will be provided to a central laboratory, instructions are provided in the Study Manual.

Triplicate 12-lead ECGs will be performed separated by approximately 1 minute at screening, on Cycle 1 Day 1 (Phase 1b, all dose levels, and Phase 2), Cycle 2 Day 1 (Phase 1b dose levels 8 through 13 and Phase 2 only) and at the EOT visit. Average QTcF will be calculated to confirm eligibility. Careful skin preparation is essential to assure high quality ECGs. All ECGs should be collected using the same ECG machines and performed in as calm an environment as possible, not immediately following stressful procedures (ie, biopsies, etc.), with minimal distractions (talking, TV, etc.). Prior to each ECG, the patient should lie in a supine position in a calm environment for at least 5 minutes.

When performed in concert with serial PK collection on Cycle 1, Day 1 for Phase 1b dose levels 1 through 7, 2 ECGs will be performed pre-dose (within 1 hour of dose, separated by at least 15 minutes). Post-dose ECGs will be performed prior to and as close as possible to each PK sample collection at approximately maximum plasma concentration (maximum plasma concentration $[C_{max}]$; 1 and 2 hours), 4 hours, and 6 hours. If possible, patients should not consume additional food between dosing and the last ECG time point.

One set of triplicate 12-lead ECGs will be performed on Cycle 1, Day 1 at 2-hours post-dose for Phase 1b dose levels 8 through 13 and Phase 2. When performed in concert with serial PK collection on Cycle 2 Day 1 for these patients, 2 ECGs will be performed pre-dose (within 1 hour of dose, separated by at least 15 minutes). Post-dose ECGs will be performed prior to and as close as possible to each PK sample collection at approximately maximum plasma concentration (C_{max}; 1 and 2 hours), 3 hours, 4 hours, 5 hours, and 6 hours.

At screening and at the EOT visit, the ECG may be performed at any time during the clinic visit. ECGs may also be performed when clinically indicated, irrespective of the time of study drug dosing.

All ECGs will be independently reviewed by a central laboratory. Instructions for the collection and transmission of ECGs to the central ECG laboratory will be provided in the Study Manual.

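### The QTc threshold counts in SAP 4.6.5.2 use routine ECG visits only, so prolongation found on a clinically indicated ECG after the last scheduled on-treatment ECG is missed unless still present at End of Treatment

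*SAP*

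**What the plan says.** **Counting rule.** SAP 4.6.5.2 summarizes QTc values above 450, 480 and 500 msec, "averaged over each set of triplicate 12-lead ECGs at each visit where ECG is routinely collected per the clinical study protocol". A separate sentence adds: "Change from baseline categories will also be summarized for measurements that represent a change >30 or >60 msec relative to the baseline value". That sentence does not repeat the routine-visit limit. SAP 4.1.2 states: "Data collected at unscheduled visits will not be included in by-visit summaries". It makes an exception for derivations that span several visits, such as a worst post-baseline value, and sends all data to the listings.

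**ECG schedule.** Protocol 7.4.2.5 places triplicate ECGs at screening, at Cycle 1 Day 1 for everyone, and then at "Cycle 2 Day 1 (Phase 1b dose levels 8 through 13 and Phase 2 only) and at the EOT visit". SAP 3.4.2.3 repeats this. The protocol also allows others: "ECGs may also be performed when clinically indicated, irrespective of the time of study drug dosing". The EOT visit is to take place as soon as possible and "within 14 days after the last dose of study drug" (Protocol 7.3.4).

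**Why QTc is watched.** Protocol 1.6.2 names it as a class effect: "Toxicities reported for other HDAC inhibitors include thrombocytopenia, QTc prolongation". Table 7 in Protocol 5.6 sets actions for QTc above 480 and above 500 msec. It lets treatment resume at the initial dose in the next cycle "provided that the QTc interval improves to ≤470 msec at the start of that cycle". Protocol 5.6.1 pauses enrolment for Grade 4 QTc prolongation.

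**The concern.** An ECG taken because QTc was in question is more likely than a routine one to be abnormal. From Cycle 3 on, every such ECG during treatment is unscheduled, and so is the recheck that Table 7 relies on at the start of a cycle. The threshold table therefore draws on the routine ECGs and omits those done for cause.

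The resulting error has one direction. The counts above 450, 480 and 500 msec can equal or understate the number of patients in whom prolongation was seen, but cannot overstate it. A patient whose treatment was interrupted in Cycle 4 for a QTc above 500 msec would be absent from the above-500 count unless the EOT ECG still showed it.

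The data set is small and final. SAP 4.8 says enrolment ended after the last Phase 1b dose level and Phase 2 will not take place. Patients deriving benefit stayed on treatment, so later-cycle exposure may well be present.

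**Working it through.** The plan states no figure to reproduce. The check sets the counting rule against the schedule and then does calendar arithmetic.

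**Inputs**
- Cycle 1 is 28 days and later cycles are 21 days (Protocol 3.1.2), so Day 1 visits fall on study days 1, 29, 50, 71 and so on.
- The last scheduled on-treatment ECG is on day 29 for dose levels 8-13 and, reading Protocol 7.4.2.5 and Table 11 note p, on day 1 for levels 1-7.
- Treatment duration T is not given. It is assumed, with a range from 56 to 364 days.

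**Step 1: scheduled coverage.** With T = 182 (26 weeks), Day 1 visits fall on days 1, 29, 50, 71, 92, 113, 134, 155 and 176, which is 9 visits. Levels 8-13 have a scheduled ECG at 2 of the 9, and levels 1-7 at 1 of the 9.

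**Step 2: share of treatment after the last scheduled on-treatment ECG.** The formula is (T − last ECG day) / T.

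| T (assumed, days) | Levels 8-13 | Levels 1-7 |
|---|---|---|
| 56 | 27/56 = 48% | 55/56 = 98% |
| 98 | 69/98 = 70% | 97/98 = 99% |
| 182 | 153/182 = 84% | 181/182 = 99% |
| 364 | 335/364 = 92% | 363/364 = 99.7% |

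In every case one more routine ECG follows, at EOT.

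**Step 3: what the EOT ECG can show.** Protocol 1.4.1.2 gives a median nanatinostat half-life of 1.8 hours as a single agent. One day after the last dose is 24/1.8 = 13.3 half-lives. An EOT ECG even a day after the last dose is a weak substitute for an on-treatment reading, as far as the parent drug goes. No half-life is given for the metabolites.

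**Step 4: weight of one patient.** Planned cohorts are 3 to 6 patients. One uncounted patient lowers a regimen's rate by 1/6 = 17 to 1/3 = 33 percentage points. This says how much one omission would matter, not how likely it is.

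**Step 5: where an unscheduled value can go.**
- Shift table: the multi-visit exception in SAP 4.1.2 lets unscheduled ECGs into the shift to the worst post-baseline result. That table uses the investigator's normal/abnormal classification, not milliseconds.
- Adverse events: Protocol 7.4.2.5 requires new or worsened clinically significant findings to be recorded as adverse events. They then enter the tables by CTCAE grade and by dose interruption (SAP 4.6.2).
- Listings: all values appear.

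None of these counts patients by millisecond category.

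**Step 6: comparison within the SAP.** SAP 4.6.4 takes laboratory shifts and toxicity grades at the worst post-baseline value and counts liver-injury criteria cumulatively. The QTc thresholds have no equivalent.

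**The case against.** The strongest objection is that such an event would not be lost. A reader might infer that QTc prolongation after Cycle 2 Day 1 is never counted. The documents do not support that. EOT is a routine ECG visit, so prolongation present then enters the threshold counts. A patient interrupted for QTc above 500 msec has a clinically significant finding that must be recorded as an adverse event, and it would show by grade and as a cause of interruption. In cohorts this small, that patient is easy to see. The enrolment pause runs through committee review of toxicities and does not depend on this table. All of this stands. What is missing is the millisecond count per patient, not all trace of the event.

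Restricting the counts to scheduled ECGs is also defensible in part. Those ECGs include readings timed near peak concentration, the single-agent study saw no apparent accumulation between Day 1 and Day 28, and for-cause ECGs have no fixed relation to dosing. That supports keeping the by-visit rows. It does not support having no per-patient maximum beside them.

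Two further limits apply. The sentence on changes above 30 and 60 msec is not clearly restricted, so the gap is certain only for the absolute thresholds. For levels 1-7, a reader might infer that Cycle 1 Day 1 is definitely the last scheduled on-treatment ECG. Section 7.4.2.5 and Table 11 note p say so, but the Table 11 grid marks Cycle 2 Day 1 without a dose-level limit and note g refers to ECGs on that day for levels 1-7. If those levels do have it, their figures become those of levels 8-13. The gap from Cycle 3 on remains either way.

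**Conclusion.** The point holds in limited form. As worded, the counts above 450, 480 and 500 msec omit unscheduled ECGs, so on-treatment prolongation found after the last scheduled on-treatment ECG is missed there unless it persists to EOT. The possible error is downward only. Over assumed durations of 56 to 364 days, the uncovered share of treatment is 48% to 92% for levels 8-13 and 98% to 99.7% for levels 1-7 on the section 7.4.2.5 reading.

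These are shares of time, not rates of missed events. The documents give no QTc event rate and do not show that any unscheduled ECG was taken, so a reader should not infer that events have in fact been missed. The shift table, adverse event tables and listings keep this from being a serious reporting failure. It is a gap in one safety table, worth closing because the remedy costs so little.

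**What to change.** In SAP 4.6.5.2:
- Keep the by-visit rows.
- Add an any-post-baseline row that counts each patient once at the maximum post-baseline QTcF (above 450, 480, 500 msec) and once at the maximum change from baseline (above 30, 60 msec). Use all scheduled and unscheduled ECGs, by dosing regimen and overall.
- State that the change categories use the same ECGs as the absolute thresholds.
- Label the row as including unscheduled ECGs, because these are taken for cause and are not timed to dosing.

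The cost is a few lines of SAP text and one table row from data already collected.

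Separately, reconcile Protocol 7.4.2.5 and Table 11 note p with the Table 11 grid and note g on whether dose levels 1-7 have a Cycle 2 Day 1 ECG, since that decides which visits count as routine. No new ECG requirement is proposed. That would be a patient-monitoring decision, and with enrolment closed it would have little effect.
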